#### 10.2.2 Utility Function

We define a utility function based the combination of the primary safety outcome,  $U_1$ , and the primary efficacy outcome,  $U_2$ , as  $U_1 \times U_2$  where 1 is perfect utility and zero is no utility. This utility score

---

provides an integrated assessment of safety (any radiographic ICH on follow-up CT) and preliminary efficacy (improvement in 24-hour NIHSS) and is used to define our “promising zone”.

For the safety outcome (ICH),  $U_1=1$  if the ICH response rate for that dose is  $\leq 40\%$  and  $U_1=0$  if the ICH rate is 70% or greater and takes a quadratic function between 40%-70%. This was based on a clinical discussion of what would be an acceptable rate of any ICH.

For the primary efficacy outcome (NIHSS), the utility equal

is defined based on the mean difference from control adjusted for baseline NIHSS.  $U_2=1$  if the dose is 2 points better than control and  $U_2=0$  if it is no different from control with a quadratic function in between 0 and 1.

### **10.2.3 Quantities of Interest**

We define quantities that will be used to make decisions during the trial.

#### *10.2.3.1 Probability of Being Target*

The  $U_{max}$  is the dose with the greatest utility (target dose). For each dose, we will calculate the probability of being the  $U_{max}$ .

#### *10.2.3.2 Posterior Probabilities for Safety*

For each dose we will calculate the probability that the ICH rate is greater than 60%. The expected ICH rate is 0.40 and 0.60 is the upper bound on the acceptable rate. We will use the probability to establish safety stopping rule.

#### *10.2.3.3 Posterior Probabilities for Utility*

For each dose we will calculate the probability that the Utility ( $U_1*U_2$ ) is greater than 0.25.

### **10.2.4 Final Evaluation Criteria**

At the final analysis, criteria for trial to be a success (‘Go’):

$$\Pr(\text{Utility} > 0.25 | \text{Greatest } U_{max}) > 80\%$$

The trial is a success if the best dose has 0.25 utility or higher with at least 80% probability.

## **10.3 Sample Size Determination**

Simulations (5000 replications) under 11 scenarios, which take the adaptive design and model assumptions into account, indicate that the probability of trial success (“power”) is 84% - 95% for all safe scenarios. A 2-point difference in NIHSS is clinically meaningful and feasibly detectable according to our simulations.

The type I error rate is shown in Table 3. Because this is an early phase trial, we opted for higher Type I error rate since this is not a pivotal trial. Under the complete null case (‘Null Safe’) all doses are the same as control on NIHSS and ICH, the probability of trial success is 0.188 (type I error rate) but was smaller if there were safety concerns. The trial stopped early in 78% of simulations when the ICH rate was unsafe (‘Null All Doses Unsafe’).

---

While higher than the 0.05 type I error rate in Phase III trials, a false positive rate of 10-20% is typically accepted in early Phase II trials; any dose arm meeting the criteria for success will be tested in a Phase III trial where the type I error rate can be tightly controlled. In early development trials, such as SISTER, the more serious error is the False Negative error and this is well controlled.

**Table 3. Design Simulation Results (Fixed and Adaptive Clinical Trial Simulator FACTSTM v6.4)**

| Scenario                    | True Mean 24-hour NIHSS
(SD=5.5) |          |     |     |      | True Proportion ICH |          |     |     |      | Proportion of
Trial
Success
"Power" | Proportion of
Trial Stop
Early for
Safety |
|-----------------------------|-------------------------------------|----------|-----|-----|------|---------------------|----------|-----|-----|------|--|--|
|                             | Placebo                             | TS23 3mg | 5mg | 7mg | 10mg | Placebo             | TS23 3mg | 5mg | 7mg | 10mg |  |  |
| Safe and Effective   |                                     |          |     |     |      |                     |          |     |     |      |  |  |
| 3 Good Doses                | 7                                   | 6        | 5   | 5   | 5    | 0.4                 | 0.4      | 0.4 | 0.4 | 0.4  | 0.95   | 0  |
| 2 Good Doses                | 7                                   | 6.5      | 6   | 5   | 5    | 0.4                 | 0.4      | 0.4 | 0.4 | 0.4  | 0.93   | 0  |
| 1 Good Dose                 | 7                                   | 7        | 6   | 6   | 5    | 0.4                 | 0.4      | 0.4 | 0.4 | 0.4  | 0.87   | 0  |
| Umbrella                    | 7                                   | 6        | 5   | 6   | 7    | 0.4                 | 0.4      | 0.4 | 0.4 | 0.4  | 0.84   | 0  |
| Unsafe but Effective |                                     |          |     |     |      |                     |          |     |     |      |  |  |
| Umbrella High Doses Unsafe  | 7                                   | 6        | 5   | 6   | 7    | 0.4                 | 0.5      | 0.6 | 0.7 | 0.7  | 0.58   | 0  |
| Bouncy High Doses Unsafe    | 7                                   | 5        | 7   | 5   | 7    | 0.4                 | 0.5      | 0.6 | 0.7 | 0.7  | 0.86   | 0  |
| Weak High Doses Unsafe      | 7                                   | 6.5      | 6   | 5   | 5    | 0.4                 | 0.5      | 0.6 | 0.7 | 0.7  | 0.29   | 0.03   |
| Weakest High Doses Unsafe   | 7                                   | 7        | 6   | 6   | 5    | 0.4                 | 0.5      | 0.6 | 0.7 | 0.7  | 0.17   | 0.04   |
| Null                 |                                     |          |     |     |      |                     |          |     |     |      | Type I Error                          |  |
| Null Safe                   | 7                                   | 7        | 7   | 7   | 7    | 0.4                 | 0.4      | 0.4 | 0.4 | 0.4  | 0.188  | 0  |
| Null High Doses Unsafe      | 7                                   | 7        | 7   | 7   | 7    | 0.4                 | 0.5      | 0.6 | 0.7 | 0.7  | 0.069  | 0  |
| Null All Doses Unsafe       | 7                                   | 7        | 7   | 7   | 7    | 0.4                 | 0.7      | 0.7 | 0.7 | 0.7  | 0.002  | 0.78   |

## **10.4 Populations for Analyses**

The primary analysis will be analyzed under the mITT principle. Under this principle, the evaluable sample will include all participants who are randomized for whom the study drug infusion was started. The Per-Protocol sample includes participants who had no eligibility violations (e.g., enrolled in error) and received their assigned study dose.

## **10.5 Conventions for Missing Data**

At any analysis, some participants may have missing data. The missing data could result from the subject dropping out of the study, or because the subject simply has not yet reached the final visit.

For any subject whose endpoint is unknown due to drop out, the final outcome will be multiply imputed from the Bayesian model. However, if a patient dies before 24 hours and their death is a neurological death (potentially informative missingness), we will impute their missing NIHSS based on the worst observed NIHSS value and as an event for the ICH outcome.

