**Endpoints:**

**Primary Endpoints:**

1. Safety: ANY intracranial hemorrhage (ICH) visualized on the CT scan 30 ( $\pm 4$ ) h after study drug administration.
2. Efficacy: NIH Stroke Scale Score at 30 ( $\pm 4$ ) h after study drug administration (adjusted for the baseline in analysis)

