## 7.3 Lost to Follow-Up

When scheduling follow-up visits, multiple attempts should be made in order to reach the participant. If the participant cannot be reached, multiple attempts should be made to the person(s) listed as secondary contact. If no contact is made after multiple attempts, alternative methods should be considered in order to obtain contact with the participant and/or verify their living status. Examples of alternative methods of contact are fax, other scheduled medical appointments, and certified letter.

**Efforts should be made for up to 150 days from randomization to determine the participants' 90-day status.** A participant may be considered lost to follow-up if they cannot be reached for up to 150 days from randomization, despite following the procedures outlined above. The following are considered to be reasons a subject is lost to follow-up: unable to contact for follow-up, moved away from and unable to return for follow-up visits. Appropriate documentation of lost to follow-up will be maintained in the subject's research record at the site.

All effort is put forth to ensure complete follow-up for all participants that had study drug initiated, in particular with the assessment of the primary outcome at 24-30 hr. This is expected to be extremely rare for patients enrolled in SISTER given that majority of the patients will be admitted to the hospital at least for the duration of 24-30 hours following their acute stroke. The study personnel will note the patient's name, date-of birth, and medical record numbers upon enrollment. They will also clearly communicate and remind the clinical care teams about the study assessment timeline to from time-to-time. Other measures taken to minimize loss to follow-up will be outlined in site-specific SOPs. It is possible that a small fraction of patients may die before completing the 30 ( $\pm 4$ ) hour assessments. Our plan to account for such missing data is outlined in the statistical analysis plan (SAP).

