### 10.2 Primary Analysis

The primary analysis will be Bayesian. We will test whether the best dose of TS23 has at least 25% Utility ("Promising Zone"). The trial is a success if the best dose has utility of 0.25 or higher with at least 80% probability. Such a utility can be achieved through various combinations of 24-hour NIHSS improvement and ICH rate.

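### The worst-score rule for early deaths covers only neurological deaths before 24 hours, while both primary endpoints are read at 30 (±4) hours

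*Protocol*

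**What the plan says.** - **Endpoint time.** The synopsis (Section 1.1) gives "Efficacy: NIH Stroke Scale Score at 30" (±4) h after study drug. Section 9.1 reads the primary safety endpoint, any ICH, on the CT at the same time. The permitted window is 26 to 34 h.
- **Default for missing outcomes.** Section 10.5: "For any subject whose endpoint is unknown due to drop out, the final outcome will be multiply imputed from the Bayesian model".
- **Exception for deaths.** The next sentence of Section 10.5, opening with 'However', reads "if a patient dies before 24 hours and their death is a neurological death (potentially informative missingness), we will impute their missing NIHSS" from the worst observed NIHSS, and counts the patient as an ICH event.
- **Deaths are expected.** Section 7.3: "It is possible that a small fraction of patients may die before completing the 30" (±4) hour assessments. It adds: "Our plan to account for such missing data is outlined in the statistical analysis plan (SAP").
- **Other 24-hour wording.** Section 10.2: "Such a utility can be achieved through various combinations of 24-hour NIHSS improvement and ICH rate". Section 10.2.2 and Table 3 also speak of a 24-hour NIHSS, while Section 10.9 uses 30 (±4) hours.
- **Population.** Section 10.4 analyses everyone randomised whose infusion was started, so early deaths stay in.

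**The concern.** The plan gives its own reason for the special rule: a neurological death is missing data that carries information. That reason applies equally to a stroke or ICH death at 25 or 30 h, yet the 24-hour limit leaves such a death out. The restriction to neurological causes also leaves out a death from systemic bleeding, although Section 2.5.1 says TS23 may increase that risk.

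The rule feeds both parts of the utility. A patient who dies of an ICH at 25 h, before the study CT, is given neither the worst NIHSS nor an ICH event by Section 10.5. The utility decides which doses later patients receive (Section 4.1) and whether the trial is declared a success (Section 10.2.4). If a dose caused extra deaths of these kinds, neither primary component would be sure to count them against it.

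**Working it through.** **1. Which deaths the rule reaches**

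| Death before the assessment | Worst NIHSS and ICH event under 10.5? | Other rule in the protocol |
|---|---|---|
| Neurological, before 24 h | Yes | Not needed |
| Neurological, from 24 h to the assessment | No | Model imputation, if death is read as drop-out; otherwise none |
| Non-neurological, at any time before the assessment | No | As above |

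The 24 h limit falls before the earliest permitted assessment. The uncovered interval for neurological deaths lasts from 26 − 24 = 2 h to 34 − 24 = 10 h, depending on when the assessment is due.

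**2. Effect of one uncovered death on an arm mean**

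Inputs from the protocol:
- 300 patients; 10 per group in the burn-in, then 13 of every 50 to control (Section 4.1).
- Control mean NIHSS 7 and SD 5.5 (Table 3).
- Full U2 at a 2-point advantage (Section 10.2.2).

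Control n = 10 + 5 × 13 = 75. Active n = 300 − 75 = 225, or 225/4 = 56.25 per dose if spread evenly.

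Assumptions: the worst score W is 25, 35 or 42, and an imputed value is near 7. The difference between scoring the death as worst and imputing it is (W − 7)/n.

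| n | W = 25 | W = 35 | W = 42 |
|---|---|---|---|
| 75 | 18/75 = 0.24 | 28/75 = 0.37 | 35/75 = 0.47 |
| 56.25 | 18/56.25 = 0.32 | 28/56.25 = 0.50 | 35/56.25 = 0.62 |
| 10 (burn-in) | 1.8 | 2.8 | 3.5 |

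The burn-in row is the raw mean, before the dose-response model smooths it.

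**3. Effect of one uncovered death on the ICH rate**

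At the expected rate of 0.40 (Section 10.2.3.2), counting an event rather than imputing adds (1 − 0.4)/n. That is 0.6/75 = 0.8 or 0.6/56.25 = 1.1 percentage points. U1 falls from 1 to 0 over 30 points (40% to 70%), so this component moves less.

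**4. An excess of uncovered deaths on active treatment**

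With an assumed active mean of 6, the harm left out of the mean is excess × (W − 6):
- 1% excess: 0.01 × 19 = 0.19 to 0.01 × 36 = 0.36 points.
- 2% excess: 0.38 to 0.72 points.

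**5. Effect on the probability of Go**

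The protocol gives no figure for this question. The nearest are in Table 3: success 0.188 under Null Safe and 0.95 under 3 Good Doses. An approximate simulation of the design, with assumed priors and three trial shapes for the quadratics, did not reproduce them. The closest version gave 0.14 and 0.92. The exact curves and priors are not in the protocol, so this says nothing against Table 3, and the results below are illustrative only (W = 35, 1,500 runs).

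| Uncovered deaths, scored as worst | Null | 3 Good Doses |
|---|---|---|
| None, or imputed as if alive | 0.14 | 0.92 |
| 1% / 2% in every arm | 0.18 / 0.20 | 0.89 / 0.88 |
| 1% / 2% excess on active | 0.08 / 0.06 | 0.83 / 0.74 |
| 1% / 2% excess on placebo | 0.27 / 0.37 | 0.95 / 0.97 |

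With an excess on active and no true benefit, imputing leaves the chance of Go at 0.14, where worst scoring would lower it to 0.08 or 0.06. An excess on placebo works the other way.

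**The case against.** The strongest reply is that Section 7.3 foresees deaths before the assessment and sends their handling to the SAP, which is not at hand. The imputation sentence names only drop-out. A reader might infer that the protocol prescribes imputing these patients as if they were alive. That is the natural reading of a death rule introduced as an exception, but the text does not say it. This part stands. The pointer does not cure the timing, though: Section 10.5 states a rule itself, and a SAP must either inherit its 24-hour limit or depart from the protocol.

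Other points that stand:
- **Bias is conditional.** A reader might infer that the primary result is biased. That needs uncovered deaths that differ by arm. With equal rates the mean difference has no expected bias, and an excess on placebo would count against TS23. The protocol gives no death rate and expects few.
- **The size depends on W.** The protocol does not say whether the worst value is the patient's own or the trial's. At W = 20 the shift is (20 − 7)/75 = 0.17. Because the analysis adjusts for baseline NIHSS, a severe patient's imputed score could exceed 7, which also shrinks the shift.
- **The 0.25 threshold.** A reader might infer that one death carries a dose across it. If U2 = 1 − (1 − d/2)², U2 reaches 0.25 at d = 2(1 − √0.75) = 0.27 points; if U2 = (d/2)², at 1.0 point. The protocol does not say which quadratic applies, and the criterion is a posterior probability after smoothing, so the inference is not supported.
- **The 72 h NIHSS.** No imputation rule is stated for it, and Section 10.8 plans no formal testing, so the point does not extend there.
- **Safety monitoring.** Deaths and major bleeding are secondary safety endpoints under independent review, so harm would be seen. It would still not necessarily enter the utility.

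Limiting the rule to neurological deaths is also partly a choice of estimand. Stopping it at 24 h has no such defence.

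**Conclusion.** The point holds as a mismatch in a stated rule. Section 10.5 protects the primary analysis only against neurological deaths before 24 h, although both endpoints are read between 26 and 34 h. Neurological deaths after 24 h but before assessment, and all non-neurological deaths before it, are either imputed like drop-outs or left without a rule.

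This may bias the NIHSS comparison and the ICH rate if such deaths differ by arm, and an excess on TS23 would go unpenalised in the utility. Each death is worth about 0.2 to 0.6 NIHSS points in a final arm mean, against 2 points for full U2. That range assumes a worst score of 25 to 42, an imputed value near 7, and arms of about 56 to 75. The simulated Go probabilities show direction only.

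**What to change.** - In Section 10.5, change the time condition to death before the 30 (±4) h assessment is obtained, for both the NIHSS and the ICH component. Keep the plan's worst-score value and state whose worst it is.
- Cover deaths from any cause under the same rule, or at least in a sensitivity analysis.
- Change the 24-hour NIHSS wording in Sections 10.2 and 10.2.2 to 30 (±4) h.
- Do not simply relabel Table 3, because those simulations are complete. State that its 24-hour mean and SD are taken to apply at 30 h, after checking that this is reasonable.

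The text changes are a few lines, and all-cause deaths are already collected (Section 9.2). They should be settled before unblinded results could influence the choice.

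The cost is a wider spread. If a fraction p of patients score W, the SD becomes √[(1 − p) × 5.5² + p(1 − p)(W − 7)²]. This gives √(29.95 + 3.21) = 5.8 for p = 1% and W = 25, and √(29.65 + 24.01) = 7.3 for p = 2% and W = 42, both rates being assumed. In the approximate simulation, which held the model SD at 5.5, equal deaths of 1% to 2% raised null success from 0.14 to 0.18–0.20 and lowered success under 3 Good Doses from 0.92 to 0.89–0.88. The operating characteristics should therefore be re-run under the revised rule.

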## **10.6 Baseline Descriptive Statistics**

A comparison of patient characteristics and at a baseline assessment between the treatment groups will be done. Baseline descriptive statistics will be provided for the following items: demographics, NIHSS, age, time from onset, prior medications, medical history, visualized occlusion status (yes/no).

## **10.7 Planned Interim Analyses**

The trial may stop early for safety (futility). No early stopping criteria for success have been defined for this trial.

## **10.8 Analysis of the Secondary Endpoints**

Secondary analyses will compare all doses to control by graphing the raw and model-fitted means and 95% CI. Group means (adjusted for baseline NIHSS and age) will be plotted with 95% confidence intervals around the mean for each dose and control. No formal hypothesis testing will be performed and no p-values reported for secondary efficacy outcomes.

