TS23 inhibited a2AP activity in all participants, in a dose-related fashion, with maximum effects in the initial blood samples after IV dosing (Figure 6A). The duration of inhibition of a2AP was also dose related. a2AP activity was  $\sim$ >50% inhibited for hours to 4 days at dose 2.5 to 7.5 mg/kg. TS23 immediately activated fibrinolysis after dosing and increased D-dimer levels relative to baseline levels; D-dimer levels were higher in cohorts receiving higher doses of TS23 (Figure 6B). (D-dimer is a specific biomarker that indicates endogenous thrombus dissolution, even in normal, asymptomatic individuals). In addition, clots formed *ex vivo* from subject plasma obtained 24h after TS23 administration rapidly dissolved in a dose-dependent fashion, while control clots from normal blood donors did not dissolve within 120 min, the maximum time of monitoring. Thus, TS23 safely engaged and inactivated a2AP, in a dose-related fashion, triggering endogenous fibrinolysis *in vivo* and clot dissolution *ex vivo*.

Figure 6. Dose-related Effects of TS23 on a2AP Activity and D-dimer Levels in Humans

A) a2AP inhibition was measured in a clinically validated plasma assay at baseline and at the indicated time points following a dose of TS23. B) D-dimer levels were measured in participants at baseline and at the indicated time points following a dose of TS23. Means  $\pm$  SE are shown for each dose cohort.

Please see the current version of the [Investigator's Brochure](#) for further information on the Phase 1 Clinical study results for TS23 (a2AP-I).

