##### **Biomarker Efficacy:**

---

1. a2AP activity at 3 ( $\pm 1$ ) h after completion of study drug administration
2. Matrix metalloproteinase-9 plasma level 3 ( $\pm 1$ ) h after completion of study drug administration.
3. % tissue reperfusion on perfusion scan obtained at 30 ( $\pm 4$ ) h after study drug administration compared to the baseline

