#### **Safety:**

1. Incidence of symptomatic ICH within 30 ( $\pm 4$ ) h of study drug administration (SITS-MOST definition) ([Wahlgren, Ahmed et al. 2007](#))
2. Incidence of non-ICH major or clinically relevant non-major bleeding within 30 days of study drug administration.
3. Non-bleeding, SAEs within 90 ( $\pm 7$ ) days
4. Incidence of stroke-related and all-cause deaths within 90 ( $\pm 7$ ) days
5. Plasma fibrinogen levels at 3 ( $\pm 1$ ) h after completion of TS23 therapy

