## 8.2 Pre-Randomization/Randomization visit

- Time of randomization
- Time of study drug administration
- Time of study drug completion
- Baseline research related laboratory studies (prior to study drug administration):
  - Fibrinogen – processed and resulted at site.
  - a2AP, MMP-9 levels and PK studies – processed and frozen. This will be shipped to the central laboratory

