## 8.4 30 ( $\pm 4$ ) Hours Post Study Drug Administration

- Research related labs:
    - Fibrinogen, PT/INR, aPTT to be processed and resulted at site
    - a2AP, and MMP-9 levels and PK studies to be processed and frozen. This will be shipped to the central laboratory
  - SOC Labs:
    - CBC
-

- NIHSS assessed by blinded, certified rater
  - Basic metabolic panel (glucose, calcium, sodium, potassium, carbon dioxide, and chloride, BUN creatinine) at 30 ( $\pm 4$ ) hours post study drug administration if done as standard of care
  - Vital Signs
  - Non contrast CT Brain (reading will be performed centrally) (**Please note that an MRI cannot substitute for the CT**)
    - ASPECTS score
    - Any radiologic hemorrhage (further classified as SAH, HI1, HI2, PH1, PH2, RIH, IVH, SDH, EDH) on CT
  - CTA or MRA head (required only if visible vessel occlusion present on the baseline CTA or MRA per site read).
    - Presence of a visible vessel occlusion
    - Location of vessel occlusion (per the central reader): ICA, M1 MCA, M2 MCA, M3/M4 MCA, A1 ACA, A2-5 ACA, VA, BA, P1 PCA, P2 PCA, P3/4 PCA, PICA, AICA, SCA, Other
  - CT/MR perfusion
    - Perfusion lesion volume (volumes of regions with  $T_{\max} > 6$  sec and  $> 10$  sec on CTP or PWI MR)
    - Ischemic core lesion volume (on CTP -volume of region with  $rCBF < 30\%$ ; on DWI-volume of region with  $ADC < 620 \times 10^{-3}$  mm/s)
    - If the participant underwent CT perfusion at baseline, then CT perfusion should be obtained at 30 ( $\pm 4$ ) hours.
    - If the participant underwent MR perfusion at baseline, then MR perfusion should be obtained at 30 ( $\pm 4$ ) hours.
  - Symptomatic intracranial hemorrhage [symptomatic ICH, as per SITS-MOST definition (a local or remote type II parenchymal hemorrhage within 30 ( $\pm 4$ ) h after treatment associated with a  $\geq 4$ -point deterioration on the NIHSS score from baseline or from the lowest score from baseline to 24 hours, or leading to death.)] ([Wahlgren, Ahmed et al. 2007](#))
  - Major non-ICH systemic hemorrhage
  - Clinically relevant systemic hemorrhage
-

- AE
- SAE
- UPs

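### Section 10.8 adjusts the 3 h biomarker means for baseline NIHSS and age only, although each marker's own pre-dose value is measured and could serve as a covariate (minor)

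*Protocol*

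**What the plan says.** Protocol section 3.2 defines the two biomarker endpoints as "a2AP activity at 3 ( $\pm 1$ ) h after completion of study drug administration" and "Matrix metalloproteinase-9 plasma level 3 ( $\pm 1$ ) h after completion of study drug administration". It lists "Plasma fibrinogen levels at 3 ( $\pm 1$ ) h after completion of TS23 therapy" among the secondary safety endpoints. None of the three refers to a baseline value.

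Section 10.8 describes the analysis of secondary endpoints in general terms: "Group means (adjusted for baseline NIHSS and age) will be plotted with 95% confidence intervals around the mean for each dose and control". It plans no formal tests and no p-values for the secondary efficacy outcomes.

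The samples are scheduled as follows:
- **Before dosing:** section 8.2 lists fibrinogen, a2AP and MMP-9 under "Baseline research related laboratory studies (prior to study drug administration".
- **At 3 h:** section 8.3 repeats the same markers.
- **At 30 h:** section 8.4 has fibrinogen resulted at site and "a2AP, and MMP-9 levels and PK studies to be processed and frozen".

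The footnotes to the schedule of activities (section 1.3) agree with these draws.

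Elsewhere in section 3.2 a baseline reference is written out where it is wanted: NIHSS at 30 h and at 72 h is adjusted for its baseline, and tissue reperfusion is compared with the baseline scan.

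**The concern.** For an outcome measured before and after treatment, the subject's own pre-treatment value is usually the strongest single covariate. For the 72 h NIHSS, the covariates in 10.8 include exactly that value. For a laboratory marker they do not: baseline NIHSS and age stand in for a pre-dose level that has been measured directly.

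The protocol gives reasons to care. Section 3.3 says the a2AP and MMP-9 measurements are meant to establish mechanistic efficacy, and describes MMP-9 as a marker tied to stroke severity, so participants can be expected to start at different levels. The same section supports the baseline-adjusted NIHSS by appeal to regression methods, and that argument carries over to a marker drawn before and after dosing.

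At stake are wider intervals than necessary around each dose-placebo difference, and a chance pre-dose difference that stays in the plotted 3 h means. Adaptive allocation can leave some dose arms small, and this matters most there.

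**Working it through.** The protocol states no SD, effect size or precision for these markers, so there is no figure of its own to reproduce. Table 3 concerns NIHSS and ICH only.

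**Arm sizes (section 4.1).** Total 300; burn-in 10 per group in five groups, so 50; then 250 / 50 = 5 blocks with 13 controls each.
- Placebo: 10 + 5 × 13 = 75.
- Active: 300 − 75 = 225, on average 225 / 4 = 56.25 per dose.
- Smallest possible dose arm if the adaptive rule sends it no one after burn-in: 10.

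**Assumption.** Let ρ be the partial correlation of a marker's pre-dose and 3 h values after NIHSS and age, the covariates already planned. The documents do not give it; I use 0.3, 0.5 and 0.7, the same in all arms. SD below means the SD of the 3 h value with NIHSS and age taken out.

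**Variance.** With the covariate, the fraction 1 − ρ² remains, so the reduction is ρ² and the equivalent gain in patients is 1 / (1 − ρ²).

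| ρ | Remaining | Reduction | Patient factor |
|---|---|---|---|
| 0.3 | 0.91 | 9% | 1.10 |
| 0.5 | 0.75 | 25% | 1.33 |
| 0.7 | 0.51 | 49% | 1.96 |

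**Half-width of the 95% interval for dose minus placebo.** 1.96 × √(1/75 + 1/n) × √(1 − ρ²).

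| Dose arm n | Without pre-dose value | ρ = 0.3 | ρ = 0.5 | ρ = 0.7 |
|---|---|---|---|---|
| 56.25 | 0.35 SD | 0.33 | 0.30 | 0.25 |
| 10 | 0.66 SD | 0.63 | 0.57 | 0.47 |

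**Chance imbalance.** The pre-dose difference between a dose arm and placebo has standard error √(1/75 + 1/n): 0.18 SD for n = 56.25 and 0.34 SD for n = 10. That is imbalance in the baseline marker. Only ρ times it reaches the 3 h comparison.

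| Dose arm n | ρ = 0.3 | ρ = 0.5 | ρ = 0.7 |
|---|---|---|---|
| 56.25 | 0.05 SD | 0.09 | 0.12 |
| 10 | 0.10 SD | 0.17 | 0.24 |

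This shift is part of the unadjusted sampling error, not an addition to it. Adjustment removes it.

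**By marker.**
- MMP-9: the gain is likely to be largest here, because no large treatment effect is stated and participants are expected to differ before dosing.
- a2AP: section 4.3 expects inhibition of roughly 50% to over 95% across the doses. Against effects of that size a chance shift matters little, and near-complete inhibition may itself weaken the link between pre-dose and 3 h values.
- Fibrinogen: it is listed under safety, while the last sentence of 10.8 speaks of efficacy outcomes, so the stated covariates reach it only through the section heading.

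**The case against.** **The SAP may settle this.** Section 10.8 is short and covers unlike outcomes; adjusted means cannot literally apply to deaths or to mRS 0–1. It does not forbid further covariates, and marker-specific models often belong in an SAP, which is not shown. This stands in part. But 10.8 names its covariates, so an SAP that followed it literally would leave the pre-dose value out. The point is an improvement to a stated choice, not a complaint about missing detail.

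**NIHSS already does some of the work.** If MMP-9 tracks stroke severity, adjusting for NIHSS captures part of the pre-dose variation. This stands, and is why ρ above is a partial correlation. Read against no adjustment at all, the same factors would overstate the gain.

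**The 30 h samples.** A reader might infer that the protocol neglects them. It does not: it schedules and collects them, and simply names no 30 h endpoint for these markers. A 3 h value suits the stated aim of mechanistic efficacy, since section 2.4 places the maximum a2AP effect in the first samples after dosing. Section 2.4 also says "The duration of inhibition of a2AP was also dose related", so showing 30 h alongside would be informative, but that is an addition to reporting and not a correction.

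**Fibrinogen.** A reader might also infer that a 3 h endpoint would miss fibrinogen loss. The documents do not support this. Section 2.2 reports no fibrinogen depletion in people with complete genetic a2AP deficiency, the 30 h fibrinogen is resulted at site, and abnormal laboratory findings can be recorded as adverse events under section 9.3.1.

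**Low consequence.** These are plotted means with intervals. They enter neither the utility, the safety stopping rule nor the Go criterion. This stands and sets the severity.

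**Conclusion.** The point holds as a minor one. Section 10.8 fixes a covariate set that omits the most direct baseline information available for a2AP, MMP-9 and fibrinogen, although the pre-dose samples are already required. Under the assumed partial correlations of 0.3 to 0.7, using them would cut the variance by 9% to 49%. It would also remove a chance shift of about 0.05 to 0.12 SD for an average dose arm, or about 0.10 to 0.24 SD for an arm left at its 10 burn-in patients, which is an extreme of the adaptive rule.

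The sizes rest on the assumed correlations, on one correlation for all arms, and on an average arm of 56 against 75 placebo. It would go too far to call the planned comparison biased: randomisation keeps it unbiased on average. Nor is it plausible that chance imbalance could pass for the large a2AP effect that the protocol expects. The trial's decision is unaffected.

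**What to change.** In Protocol section 10.8, and in the SAP accordingly, add that the 3 h analyses of a2AP activity, MMP-9 and fibrinogen also include the participant's own pre-dose value of that marker as a covariate, with MMP-9 on the log scale before and after dosing. Name fibrinogen explicitly, so that its adjustment does not depend on the section heading.

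Optionally, report the 30 h values beside the 3 h values as supportive, keeping 3 h as the main time point.

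The cost is wording only; no sample or visit is added. The one downside is that some pre-dose tubes will be missed, so a simple rule for a missing pre-dose value should be stated in advance.
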